2.6 Participant Risks

Rare

- Dizziness or passing out
- Hard stools (constipation)
- Loose stools (diarrhea)
- Upset stomach or throwing up
- Feeling sleepy
- Feeling tired or weak
- Not able to sleep

Rare but serious adverse events that have been reported

- Chest pain that is new or worse
- Change in thinking clearly and with logic
- Hallucinations
- Memory problems or loss
- Mood changes
- A burning, numbness, or tingling feeling that is not normal
- Change in eyesight
- Shortness of breath, a big weight gain, swelling in the arms or legs
- Any bruising or bleeding
- Slow heartbeat
- A heartbeat that does not feel normal
- Feeling cold
- Low blood sugar, signs may include dizziness, headache, feeling sleepy, feeling weak, shaking, a fast heartbeat, confusion, hunger, or sweating.
- A very bad skin reaction (Stevens-Johnson syndrome/toxic epidermal necrolysis) may happen. It can cause very bad health problems that may not go away, and sometimes death. Get medical help right away if you have signs like red, swollen, blistered or peeling skin (with or without fever), red or irritated eyes, or sores in your mouth, throat, nose, or eyes.
- In some cases if you stop taking propranolol all of a sudden you may develop chest pain that is worse and in some cases a heart attack may occur. This risk may be greater if you have certain types of heart disease. To avoid side effects, do not stop taking propranolol all of a sudden, you want to slowly stop this drug as ordered by your doctor. Call your doctor right away if you have new or worse chest pain or if other heart problems occur.

Allergic Reactions

Allergic reaction, such as rash; hives; itching; red, swollen, blistered or peeling skin with or without fever; wheezing; tightness in the chest or throat; trouble breathing or talking; unusual hoarseness; or swelling of the mouth, face, lips, tongue or throat

In some cases if you stop taking propranolol all of a sudden you may develop chest pain that is worse and in some cases a heart attack may occur. This risk may be greater if you have certain types of heart disease. To avoid side effects, do not stop taking propranolol all of a sudden, you want to slowly stop this drug as ordered by your doctor. Call your doctor right away if you have new or worse chest pain or if other heart problems occur.

The FDA black box warning:

In some cases if the patient stops taking propranolol all of a sudden the patient may develop chest pain that is worse and in some cases a heart attack may occur. This risk may be greater if the patient has certain types of heart disease. To avoid side effects, do not stop taking propranolol all of a sudden, if the patient wants to slowly stop this drug as ordered by their doctor. The patient should call the doctor right away if the patient has new or worse chest pain or if other heart problems occur.

3.0 STUDY ENDPOINTS

3.1 Primary Endpoint

Expression levels of beta-adrenergic mediated gene expression will be compared between individuals randomized to propranolol vs. control just prior to HCT as well as 28 days following autologous HCT for MM. Quantification of whole genome RNA production will be performed with specific identification of expression of beta-adrenergic signaling pathways.

3.2 Secondary Endpoints

3.2.1 Gene expression

3.2.1.1 Gene expression based on psychosocial factors

Expression levels of beta-adrenergic mediated gene expression will be compared between individuals with high vs. low levels of depression and anxiety, defined as a score of 8 or above on the Hospital Anxiety and Depression Scale (HADS) anxiety (HADS-A, 7 items) and depression subscales (HADS-D, 7 items)⁴² at all three blood draw timepoints. Expression differences will be assessed both dependently and independently of treatment group assignment.

3.2.2 Clinical

3.2.2.1 Feasibility

The feasibility portion of the study is the test of whether patients undergoing autologous HCT for MM can be placed and maintained on a beta-blocker during the immediate peri-transplant period. Feasibility to use propranolol in autologous MM HCT recipients for the adjunct cancer control purposes will be determined by a 55-70% enrollment rate and 65-70% retention rate as described below in sections 3.2.2.1a-b. The study intervention will be deemed feasible if both of the below parameters for enrollment and retention are met.

3.2.2.1a Enrollment rate

Based on similar biobehavioral cancer research efforts at other institutions, the target enrollment rate is 55-70%. Of all eligible patients that are approached, the goal is that 55-70% will provide informed consent and enroll in the study. This target rate also takes into account the possibility that enrollment may be slightly lower due to the present study being a drug intervention trial with potential patient reticence to enroll.

3.2.2.1b Retention rate

Based on similar research and the nature of drug intervention trials (as described in 3.2.2.1a), the target retention rate is 65-70%. Retention rate will be assessed individually for two time periods - prior to transplant (between Time 1 and Time 2) and from transplant through Day +30 (Time 2 to Time 3). This allows for assessing the impact on gene expression in both a run-in period preceding transplantation as well as during the transplant process, whereby there will be a greater number of confounding variables that may potentially impact gene expression and adherence. Participants will be considered to be retained in the study for the given time period assessment if they are 80% adherent to their prescribed dose of medication during the specified time period.

Drug adherence will be measured as a percentage of the prescribed number of pills that were actually taken (either 20 mg or 40 mg twice daily). This will be determined outpatient via pill count on Day -2 and Day +28 and inpatient through nursing documentation. Patients will have one additional pill count upon return of the study supply of propranolol. The return will occur at the next earliest clinic appointment following discontinuation of the propranolol. There is no consensual standard for what constitutes adequate adherence. Clinical trials report average adherence rates of 43 to 78 percent among patients taking drugs for chronic conditions; some clinical trials define rates above 80% as acceptable.⁴³ A target adherence rate of 80% will be utilized in this study to constitute having adequately retained the patient in the study. Adherence will be recorded as a continuous (0-100%) variable. Adherence will be assessed separately during two time periods – prior to transplant (between Time 1 and Time 2) and from transplant through Day +28 (Time 2 to Time 3). Patients will be included in final analyses if and only if they have been adherent (at least 80% of the prescribed dose) to the study drug during the designated time period.

As the retention rate (participants' ability or inability to be maintained on the study drug) will necessarily be affected by side effects, we will collect side effect data to better

inform the feasibility aim of this study. Common side effects that will be screened for clinically at follow up time points include fatigue, dizziness, constipation, bradycardia, hypotension, depression, insomnia, weakness, disorientation, nausea, diarrhea, hypersensitivity reaction, purpura, alopecia, and impotence. Any side effects deemed secondary to beta-blocker usage will be documented and appropriately treated or referred for treatment collaboratively by the study PI and treating HCT physician, and beta-blocker therapy will be weaned by 20 mg at each dosing time. Patients will remain at the weaned dose for 1 week prior to discontinuing if this dose decrease does not eliminate the drug entirely. Heart rate and blood pressure will be monitored and documented at baseline, once after initiating beta-blocker therapy but before transplant, just prior to transplant, and weekly thereafter; these are two of the most common and dangerous side effects. Given that patients aren't as acutely medically ill pre-transplant and that standard of care following beta-blocker initiation would involve follow-up weeks later, this schedule should allow for adequate study drug monitoring while minimizing patient study visit burden. Blood pressure less than 90/55 or heart rate less than 50 will prompt clinical review by the study PI and treating HCT physician for appropriateness to continue beta-blocker therapy. Calendar collection of adverse events (AEs) will be obtained through toxicity forms (Common Terminology Criteria for Adverse Events [CTCAE]) completed weekly until neutrophil engraftment occurs (absolute neutrophil count $> 500/\text{mm}^3$ for ≥ 3 consecutive days) and bi-weekly thereafter until the study endpoint at Week 6 (See Tables 2a and 2b). Further details about AE monitoring are included in Section 4.3.

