5.2 Sample Size and Power Calculation

We will enroll 40 participants undergoing autologous HCT for MM at MCW. Accounting for study attrition and beta-blocker intolerance, we aim to have 30 patients with a complete set of gene data. A sample size of 40 will inform our feasibility aim, while a targeted final sample of 15 participants in the intervention group will be sufficient for gene expression analysis. The gene expression sample size is based on previous studies with similar or smaller sample sizes that have evaluated gene expression as a function of psychosocial factors and yielded hundreds of differentially expressed genes that generate statistically significant results in higher-order bioinformatics.^{35, 45, 46} More specific sample size estimates are difficult to project with any greater accuracy, as there is not data on the effect size for gene expression differences as a function of propranolol in humans. To this end, the current proposal will inform future sample size estimations. This study is intended mainly to generate effect size estimates and 95% confidence intervals to aid with planning future research projects. We will generate both simple estimates of effect size as well as adjusted estimates, attempting to control for any accidental confounding that may occur despite randomization.

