5.4.2 Clinical

5.4.2.1 Feasibility

Feasibility to use propranolol in autologous MM HCT recipients for the adjunct cancer control purposes will be determined by a 55-70% enrollment rate and 65-70% retention rate as described in section 3.2.2.1. The rates of these events will be tabulated.

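### The feasibility criterion is written as two-sided bands, so read literally only 13 or 14 of 20 retained passes, the plan's own target of 15 does not, and the intended minimum is not fixed.

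*Combined protocol and SAP*

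**What the plan says.** Section 3.2.2.1 gives the rule: feasibility "will be determined by a 55-70% enrollment rate and 65-70% retention rate". It then says how the verdict is reached: "The study intervention will be deemed feasible if both of the below parameters for enrollment and retention are met". Section 5.4.2.1 repeats the ranges ("will be determined by a 55-70% enrollment rate and 65-70% retention rate as described in section 3.2.2.1") and adds that the rates will be tabulated.

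The subsections of 3.2.2.1 use softer language. For enrollment, among eligible patients approached, "the goal is that 55-70% will provide informed consent and enroll in the study". For retention, "the target retention rate is 65-70" per cent. Patients count as "retained in the study for the given time period assessment if they are 80% adherent to their prescribed dose of medication" in the period concerned. Retention is assessed separately before transplant and from transplant onward.

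Section 5.2 sets a different figure for the same arm: "a targeted final sample of 15 participants in the intervention group will be sufficient for gene expression analysis". Sections 3.2.2.1b and 5.3.1 limit the analysis of propranolol patients to those at the 80% adherence level, the same threshold that defines retention.

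**The concern.** A feasibility criterion should become easier to meet as consent and retention improve. A band does the opposite above its upper end, and no sentence in 3.2.2.1 or 5.4.2.1 says what follows when a rate exceeds 70%. The retention band is only five percentage points wide, and in an arm of 20 each patient is worth five points. It therefore admits two outcomes, and the number of evaluable patients the plan hopes for is not one of them.

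Feasibility is a stated secondary objective (section 2.2), and section 5.2 says the sample of 40 is meant to inform it. The study is unblinded (section 4.1). If the rule does not fix one cut in advance, the choice can be made after the retention count is known.

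**Working it through.** **Inputs.** Bands of 55-70% and 65-70% (3.2.2.1, 5.4.2.1). Planned enrollment of 40, 20 per group (4.1). Target of 15 intervention patients, and 30 overall with complete gene data (5.2). Retained means 80% adherent to prescribed pills (3.2.2.1b). The retention denominator is not named; I take it as the 20 propranolol patients, because only they have pills to count.

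**The plan's own figure.** 15/20 = 75% and 30/40 = 75%. No loss rate is stated, but a 25% loss reproduces both sizes: 15/0.75 = 20 and 30/0.75 = 40. Section 5.2 is thus internally consistent at an implied 75% evaluable.

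**Counts inside the retention band.** 0.65 × 20 = 13 and 0.70 × 20 = 14. On either side, 12/20 = 60% and 15/20 = 75%. Only 13 and 14 pass.

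**Probability of passing in one period.** With X ~ Binomial(20, p), the band passes with probability P(X = 13) + P(X = 14), and a minimum of 13 passes with P(X ≥ 13). The true rates are illustrative.

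| True retention p | Band (13 or 14) | Minimum of 13 | 15 or more |
|---|---|---|---|
| 65% | 0.356 | 0.601 | 0.245 |
| 70% | 0.356 | 0.772 | 0.416 |
| 75% | 0.281 | 0.898 | 0.617 |
| 80% | 0.164 | 0.968 | 0.804 |
| 90% | 0.011 | 0.9996 | 0.989 |

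The band's pass probability is about 0.37 at best (0.366 at p = 67.5%) and falls as retention improves. If both periods had to pass, were independent and used 20 patients, the best case would be 0.366² = 0.13.

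**Which minimum?** At p = 70%, P(X = 13) = 77,520 × 0.7¹³ × 0.3⁷ = 0.164. A minimum of 14 therefore passes with probability 0.772 − 0.164 = 0.61, against 0.77 for a minimum of 13. With exactly 13 retained, the verdict depends on which end of the range is used.

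**Retention range against the target of 15.** 65-70% of 20 is 13-14, short of 15. To reach 15 at those rates the arm would need 15/0.70 = 21.4, so 22, up to 15/0.65 = 23.1, so 24.

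**Sensitivity to the denominator.** For any denominator of 20 or fewer, 15 retained is at least 75%, above the band. With 14 or 17 patients at risk in the second period, no whole number lies within 65-70% (9.1 to 9.8, and 11.05 to 11.9). On all 40 participants the band is 26-28, and the target of 30 (75%) is still outside.

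**Enrollment.** With 40 enrolled, 40/0.70 = 57.1 and 40/0.55 = 72.7, so the band is met only if 58 to 72 eligible patients were approached. Enrolling 40 of 57 (70.2%, unrounded) or of fewer would fail as written.

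**The case against.** The strongest reply is that nobody would apply the upper limit. Section 3.2.2.1 calls the ranges a target and a goal, and a target is ordinarily met when it is exceeded. The only departure it discusses is lower enrollment. It frames feasibility as whether patients can be put and kept on the drug, and retaining 16 of 20 cannot count against that. This stands as evidence of intent: a minimum was probably meant. It does not settle the rule, because a range offers two candidate minimums and the text chooses neither.

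Four stronger readings are tempting and are not supported:

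- A reader might infer that this is the protocol's only go/no-go rule. Appendix B contains a safety stopping rule, and no stated action follows from the feasibility verdict.
- A reader might infer that the trial would wrongly be called not feasible 84% of the time (1 − 0.16). That needs both a true retention of 80%, which the documents do not give and which exceeds their own 65-70% expectation, and an investigator who applies the upper limit literally.
- A reader might infer that the plan needs 15 patients. Section 5.2 states 15 as a target that would be sufficient.
- A reader might treat the 15 and the retention count as the same quantity. The 15 concerns complete gene data after attrition and intolerance; retention is adherence assessed by period. They are linked through the 80% threshold.

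**Conclusion.** The point holds as a defect in the stated criterion. Read literally, the retention band passes only 13 or 14 of 20 and excludes the 15 that section 5.2 aims for. Read as a minimum, it leaves the verdict at 13 of 20 undetermined and still sits below the implied 75%. For one period at 70% true retention, the pass probability is 0.36 (band), 0.77 (minimum of 13) or 0.61 (minimum of 14); at 80% it is 0.16 for the band and 0.97 for a minimum of 13.

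The probabilities assume a denominator of 20, independent patients and a single period. The conflict with the target of 15 does not depend on the first of these, since it persists for smaller denominators and for all 40. It does assume that the 15 are counted after the adherence restriction. The documents do not say whether both periods must pass.

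The consequence is limited: feasibility is a secondary endpoint of a pilot, and the tabulated rates will let readers see the actual retention. But a prespecified threshold that gives a wrong or undetermined verdict should be corrected.

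**What to change.** In sections 3.2.2.1 and 5.4.2.1, before data are seen:

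- Replace the bands with one-sided minimums and no upper limit, for example enrollment of at least 55% and retention of at least 65%, the lower ends of the stated ranges.
- Name the retention denominator for each period, and say whether both periods must pass.
- Reconcile the retention figure with section 5.2. Either state that 13-14 retained would be feasible but below the gene-expression target of 15, or restate that target as 13-14.

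This takes a few sentences and needs no change to conduct or sample size. It does have a cost: the sponsor must commit to one of two possible cuts, and a stated figure may become slightly less favourable.

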3.2.2.2 Outcomes

- Depression and anxiety: as assessed by the HADS, with scores of 8 or above on HADS-A (7 items) and HADS-D (7 items) defining significant anxiety or depression, respectively.⁴² Depression and anxiety will be described both overall and between treatment vs. control groups.
- Engraftment syndrome: presence of fever, diarrhea, or rash within 48 hours before or after neutrophil recovery that requires steroids for treatment. This will be determined at the discretion of the treating physician and will be categorized as yes/no.
- Neutrophil engraftment: time to absolute neutrophil count (ANC) $> 0.5 \times 10^9/\text{L}$ sustained for three consecutive assessments at least one day apart.
- Platelet engraftment: time to achieve a platelet count of (a) $> 20 \times 10^9/\text{L}$ independent of platelet transfusions for 3 consecutive assessments at least one day apart.
- Infection: number of documented culture positive infections or neutropenic fever episodes defined as fever > 100.4 degrees F.
- Response to treatment: The trial will assess the rates of very good partial response (VGPR) or better (near complete response (nCR), CR, and stringent CR (sCR)) according to the International Uniform Response Criteria at day 100 post-HCT.
- Treatment-Related Mortality (TRM): TRM is defined as death occurring in a patient from causes other than disease progression. TRM will be assessed at D100

for both the intervention and control arms. Patients alive and progression-free at 100 days will be censored.

- **Progression-Free Survival (PFS):** Progression (for patients not in CR) is defined as increase of serum paraprotein by 0.5 g/dL compared to pre-transplant levels, increase in 24 hour urine protein electrophoresis ≥ 200 mg compared to pre-transplant levels, absolute increase in the difference between involved and uninvolved FLC levels of >10 mg/dl (only in patients without measurable paraprotein in the serum and urine), $>25\%$ increase in plasma cells in a bone marrow aspirate or on trephine biopsy (must also be an absolute increase of at least 10%), increase in the size of existing bone lesions or soft tissue plasmacytomas, development of new bone lesions or soft tissue plasmacytomas, development of hypercalcemia (corrected serum Ca >11.5 mg/dL or >2.8 mmol/L) not attributable to any other cause. Development of a compression fracture does not exclude continued response and may not indicate progression. PFS will be compared between the two arms as a time to event endpoint censored after 100 days of follow-up on each patient. Patients are considered a failure of the primary endpoint if they die or suffer from disease progression. The time to this event is the time from randomization to progression, death, loss to follow up or Day 100 - whichever comes first.
- **Overall Survival (OS):** The event is death from any cause. The time to this event is the time from randomization to death, loss to follow-up or the end of 100 days, whichever comes first. Patients alive at the time of last observation are considered censored. Estimates of OS will be described for each group at 100 days post-transplant.

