4.2 Baseline Demographic-, Disease-, and Treatment-Related Variables

Patient-related:

- Age at transplant
- Gender
- Race: Caucasian vs. African American vs. Asian/Pacific Islander vs. Other
- Body Mass Index: <18.5 vs. 18.5-24.9 vs. 25-29.9 vs. >=30
- Smoking status in 3 months prior to HCT (Y/N)
 - Household income prior to disease diagnosis: <\$23,000, \$23,000-\$34,999, \$35,000-\$44,999, \$45,000-\$54,999, \$55,000-\$64,999, \$65,000-\$74,999, >\$75,000
- Number of individuals in patient's household
- Education level: < high school vs. high school graduate vs. some post high school education vs. college degree vs. professional degree

Disease-related:

- International Stage
- Disease status prior to transplant: complete response, very good partial response, partial response, or stable disease
- Cytogenetics: high risk vs. standard risk by International Myeloma Working Group (IMWG) criteria

Treatment-related:

- Number of CD34+ cells infused/kg of recipient body weight
- Transplant setting: inpatient vs. outpatient transplant (defined as patients who plan to stay outpatient during entire transplant period)

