5.4.2.2 Outcomes

- Depression and anxiety: HADS scores will be tabulated and evaluated comprehensively as well as by HADS-A and HADS-D. The trajectory of these scores over the course of the study will be described. Differences in scores between the treatment vs. control groups over the course of the study will be assessed.
- Engraftment syndrome: Engraftment syndrome occurrences will be tabulated and the incidence described for both treatment and control arms.
- Neutrophil engraftment: Differences in time to neutrophil engraftment will be determined between treatment and control arms.
- Platelet engraftment: Differences in time to platelet engraftment will be determined between treatment and control arms.
- Infection: Infection events will be tabulated and differences in events will be determined for treatment and control arms.
- Response to treatment: The rates of VGPR or better (nCR, CR, and sCR) will be calculated at 100 days post-transplant and compared between intervention and control arms.
- Treatment-Related Mortality (TRM): TRM is defined as death occurring in a patient from causes other than disease progression. Disease progression is a competing event for TRM. The time to this event is the time from randomization to death, disease progression, loss to follow-up or the end of 100 days post-transplant, whichever comes first. Patients alive without disease progression at 100 days are considered censored. The cumulative incidence of TRM at 100 days will be estimated separately for each treatment-group. Overall TRM through 100 days of follow-up will be compared using Gray's test.
- Progression-free survival (PFS): PFS will be compared between the two arms as a time to event endpoint censored after 100 days of follow-up on each patient. Patients are considered a failure of the primary endpoint if they die or suffer from disease progression. The time to this event is the time from randomization to progression, death, loss to follow up or Day 100 - whichever comes first. The Kaplan-Meier estimate of survival will be estimated separately for each treatment group at 100 days post-transplant.
- Overall survival (OS): The event is death from any cause. The time to this event is the time from randomization to death, loss to follow-up or the end of 100 days, whichever comes first. Patients alive at the time of last observation are considered

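### Progression is defined only for patients not in CR, with no rule for relapse from CR, and its serum and urine criteria look back to the pre-transplant level, so some relapses may be missed in PFS and TRM.

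*Combined protocol and SAP*

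**What the plan says.** The PFS entry in section 3.2.2.2 opens with "Progression (for patients not in CR) is defined as increase of serum paraprotein by 0.5 g/dL compared to pre-transplant levels". It then lists alternative criteria:

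- Urine: "increase in 24 hour urine protein electrophoresis ≥ 200 mg compared to pre-transplant levels".
- Free light chains: "absolute increase in the difference between involved and uninvolved FLC levels of >10 mg/dl", restricted to patients with no measurable paraprotein in serum or urine.
- Marrow: a rise in plasma cells of more than 25%, which "must also be an absolute increase of at least 10" percentage points.
- Lesions and calcium: growth of existing lesions, and "development of new bone lesions or soft tissue plasmacytomas, development of hypercalcemia".

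The PFS event is progression or death, with time running to Day 100 at most. Section 5.4.2.2 repeats the event and adds no definition.

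Three other places bear on this. Section 4.2 records "Disease status prior to transplant: complete response, very good partial response, partial response, or stable disease", so CR at transplant is foreseen. The response entry in 3.2.2.2 counts CR and stringent CR among responses of VGPR or better, judged "according to the International Uniform Response Criteria at day 100 post-HCT". For TRM, section 5.4.2.2 states: "Disease progression is a competing event for TRM".

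**The concern.** A progression rule that excludes patients in CR needs a companion rule for relapse from CR, and there is none. The response criteria cited for the Day 100 response rate are not cited for progression or relapse, so a reader cannot assume that they fill the gap.

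The reference level raises a second problem. A patient whose paraprotein falls after transplant and then climbs again is compared with the value before the fall. The deeper the response, the larger the later rise that the serum and urine criteria leave uncounted.

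What is at stake is event classification for PFS, and for TRM through its competing event. A CR patient whose relapse is not recognised stays in the TRM risk set. The study is unblinded (section 4.1), so leaving relapse from CR to individual judgement also allows inconsistent calls. Section 5.2 says that the study mainly serves to produce effect estimates for planning later research, and an event definition with a hole in it could be carried forward.

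**Working it through.** The documents give no PFS rate, event count, hazard ratio or power, so there is no figure to reproduce. The check is of the definition, with simple arithmetic for the reference level.

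**Step 1: who is covered.** Section 4.2 allows CR before transplant, and section 3.2.2.2 allows CR or stringent CR after it. The progression rule applies to patients not in CR but does not say when that status is judged. Three readings are possible:

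- *Judged before transplant.* Patients in CR at transplant have no progression definition. Patients who reach CR later stay under the rule, but their serum and urine values are compared with the pre-transplant level.
- *Judged by the response reached after transplant.* Patients who reach CR after transplant also fall outside the rule.
- *Judged at the assessment in question.* A patient who has lost CR comes back under the rule, again with the pre-transplant reference for serum and urine.

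The text does not choose between these. On the first two, some or all CR patients have no stated PFS event except death.

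**Step 2: which criteria look back to the pre-transplant level.**

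| Criterion | Stated reference |
|---|---|
| Serum paraprotein | Pre-transplant |
| 24-hour urine | Pre-transplant |
| Free light chains | None stated |
| Marrow plasma cells | None stated |
| Growth of existing lesions | None stated |
| New lesions, hypercalcemia | Not tied to a pre-transplant level |

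Only the first two carry the pre-transplant reference.

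**Step 3: size of the serum effect.** Let P be the pre-transplant level and N the post-transplant low, in g/dL. The criterion is met at P + 0.5, so the rise needed from the low is (P + 0.5) − N. The documents give no paraprotein values; P and the percentage falls below are assumed.

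| P | Trigger P + 0.5 | N after 50% fall | Rise needed | N after 90% fall | Rise needed |
|---|---|---|---|---|---|
| 1.0 | 1.5 | 0.5 | 1.0 | 0.1 | 1.4 |
| 2.0 | 2.5 | 1.0 | 1.5 | 0.2 | 2.3 |
| 3.0 | 3.5 | 1.5 | 2.0 | 0.3 | 3.2 |

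For example, a patient going from 2.0 to 0.2 and then to 1.5 has risen 1.5 − 0.2 = 1.3 from the low, but stands at 1.5 − 2.0 = −0.5 against the reference. The serum criterion is not met. Whether the patient counts as progressed then depends on the other criteria.

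**Step 4: how many patients.** The documents do not give the CR share. If 10% to 50% of the 40 patients were in CR (assumed), 0.10 × 40 = 4 to 0.50 × 40 = 20 patients could have no applicable definition.

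**Step 5: what can be observed.** Table 4.7b marks myeloma response assessment at Day 100 only, and PFS is censored at Day 100. With one pre-transplant value and one Day 100 value there is no earlier post-transplant low, and the choice of reference changes nothing. It matters only for patients with interim values in the medical record, to which section 4.1 obtains access by consent.

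**The case against.** The strongest reply is that this is a gap in wording with little practical reach. PFS is one of many secondary outcomes in a 40-patient pilot, and section 5.4.2.2 names no test for it. CR after transplant is scheduled for assessment at the same point where PFS ends, so a relapse from post-transplant CR would seldom be seen inside the window. The practical gap is mainly patients already in CR at transplant. The pre-transplant reference is stated openly, and the documents do not reproduce any standard that requires the lowest value instead. All of that stands, and it limits the weight of the point.

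It does not close the gap. CR at transplant is a listed baseline category, and those patients are at risk of a PFS event from randomization.

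Two stronger readings are tempting and are not supported:

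- A reader might infer that every criterion uses the pre-transplant level, so that no relapse after a response is an event. Only serum and urine do. A patient not in CR still has an event through lesions, hypercalcemia, a qualifying marrow rise, a free light chain rise where that criterion applies, or paraprotein 0.5 g/dL above the pre-transplant level.
- A reader might infer that relapse from CR is expressly ruled out as an event. It is undefined. The literal text does not capture it, but an assessor could still call it progression, and different assessors could decide differently.

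**Conclusion.** The point holds in this form. The only progression rule leaves out patients in CR, although the protocol foresees them, and nothing else defines relapse for them. Read literally, their relapse counts neither in PFS nor as the competing event for TRM. Separately, the serum and urine criteria can miss a biochemical rise from a post-transplant low where interim values exist.

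The effect is probably small. PFS is secondary and ends at 100 days, myeloma assessment is scheduled once, and the primary CTRA analysis is unaffected. The 4 to 20 patients and the paraprotein examples rest on assumed inputs. A reader might conclude that Day 100 PFS is overstated by a known amount, or more in one arm. The documents give neither CR shares nor event counts, so neither the size of any bias nor a difference between arms can be established. The point merits correction because a foreseen group lacks an event definition and the remedy is cheap.

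**What to change.** Amend the PFS entry in section 3.2.2.2 as follows:

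1. Add a definition of relapse from CR, taken from the International Uniform Response Criteria already used there for response, and write it out in the protocol.
2. State that the listed lesion, plasmacytoma, marrow and calcium criteria apply to patients in CR as well.
3. State when CR status is judged.
4. For serum paraprotein and 24-hour urine, compare with the lowest value recorded from pre-transplant onward.
5. In section 5.4.2.2, say that the same definition determines the competing event for TRM.

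It would also help to give a reference value for the free light chain and marrow criteria, which now have none.

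The cost is protocol wording and, for item 4, extraction of any interim values from the medical record. No extra visit or patient is needed, but item 4 has effect only where such values exist, because the schedule does not require them. The downside is that Day 100 PFS may look slightly less favourable.
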